Office-based buprenorphine treatment could be expanded substantially to treat many Americans with an opioid use disorder who are not in treatment. As of 2016, physicians who have an addiction specialty board certification or who have completed an 8-hour course, and nurse practitioners and physician's assistants who have completed an extended course, may receive a waiver to prescribe buprenorphine. Once approved to serve as a buprenorphine provider, medical professionals can prescribe many doses of buprenorphine per prescription, often in 30-day supplies (Schuckit, 2016).

Buprenorphine diversion. Because office-based buprenorphine providers can prescribe 30-day supplies of buprenorphine at a time and are not required to observe daily buprenorphine dosing (as is done in methadone maintenance treatment programs), buprenorphine doses can be diverted easily. Diversion increases the availability of illicit buprenorphine on the street, diminishes the effectiveness of office-based buprenorphine treatment, and increases the risk that buprenorphine providers may be contributing to problems associated with buprenorphine diversion. The risk of diversion also may limit the expansion of office-based buprenorphine treatment. Many eligible medical professionals do not apply for the waiver to become buprenorphine providers, and many providers do not prescribe to capacity (DeFlavio et al., 2015; Huhn and Dunn, 2017; Kundsen, 2015; Sharma et al., 2017). In surveys examining barriers to prescribing buprenorphine, physicians have raised concerns about illicit diversion of buprenorphine (Andrilla et al., 2017; Johanson et al., 2012; Schuman-Olivier et al., 2013). Indeed, diversion of buprenorphine is a serious and growing concern (Cicero et al., 2014; Johanson et al., 2012). A recent large-scale, national survey reported that misuse of buprenorphine has increased substantially, and that over one-third of the buprenorphine misusers in the sample had used by the intravenous route; respondents reported that they had injected buprenorphine/naloxone tablets and film after using methods that they believed separated the buprenorphine from naloxone (Cicero et al., 2014).

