Participants will be randomly assigned to a Usual Care Control or Video DOT+ group. A computerized urn randomization procedure (Wei & Lachin, 1988) will be used to randomize participants and to balance groups on two baseline characteristics that may influence outcome: (1) sex (male/female) and (2) intake urine sample positive for cocaine (Yes/No). Participants will be stratified based on sex and evidence of cocaine use because each has been associated with buprenorphine treatment outcomes (Marsch et al., 2005; Sullivan et al., 2010). While it might be desirable to stratify on other variables, increasing the number of variables is not practical given the sample size proposed for this study.

STUDY 2

Computer-Based Education Program

Upon enrollment in Study 2, participants will be taught how to use the Video DOT application through a computer-based education program. All participants who are eligible for Study 2 will be invited to complete the computer-based program. After participants complete the computer-based program, they will be invited to participate in a 7-day smartphone induction period (as described in detail below).

Course Content. The content of the computer-based program was developed using screenshots of the different sections of the study smartphone app. The program teaches participants the main functions of each setting in the app while using the screenshots as a visual aid.

Computer-Based Education Program. The course is divided into Modules consisting of Presentation and Mastery Units. Presentation Units were designed to introduce new material, while Mastery Units allow participants to practice answering questions about that material. Each Mastery Unit consists of a series of question screens with questions about the content in the previous Presentation Unit. Question

Date: February 11, 2020

Principal Investigator: [name]

Application Number: IRB00186156

screens may be presented in random order in a one-minute practice trial (i.e., “timing”). Participants will be able to earn \$30 for completing the computer-based education program.

Smartphone Induction

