Assessments will be conducted at intake, every 4 weeks during the 24-week intervention period, and at a 12-week follow-up period. Participants will be paid \$50 for completing each of the assessments. These assessments may be collected using Qualtrics or REDCap.

Intake Only Assessment Instruments

DSM-5 Checklist for Opioid Use Disorder. The DSM-5 checklist for opioid use disorder is a structured assessment that will be used to determine if participants have opioid use disorder.

Treatment Facilitators and Barriers Questionnaire. This questionnaire will assess participants' self-reported barriers and facilitators to accessing opioid use disorder treatment.

Intake and Major Assessment Instruments

Urine toxicology testing. Urine samples will be collected under observation and tested for opioids and other drugs.

Smartphone Form. This questionnaire will document participants' access to and willingness to use a smartphone during the study.

Time-line follow-back (TLFB). Participants will be asked whether or not they are in treatment for their opioid use disorder, including treatment other than buprenorphine (e.g., methadone maintenance). For participants who report being in buprenorphine treatment, the TLFB procedure will be used to elicit participants' self-reported taking of their buprenorphine dose each day. Pharmacy and/or clinic records (with participant permission) may be used to confirm self-reported data.

Opioid Overdose Risk Assessment. An opioid overdose risk assessment will be used to assess the rate at which participants report engaging in behaviors that may put them at risk for an opioid overdose.

The Addiction Severity Index – Lite (ASI-Lite). The ASI-Lite is a structured interview designed to assess problem severity in areas commonly affected by drug and alcohol use (medical, legal, employment, family/social, and psychiatric) with good reliability and validity.

The Beck Depression Inventory (BDI). The BDI is a 21-item questionnaire designed to screen for severity of depression.

Treatment Acceptability Questionnaire. To assess the acceptability of our intervention, we will administer a Treatment Acceptability Questionnaire to participants who are exposed to our smartphone incentive intervention at the end of the 24-week intervention period.

- b. Study duration and number of study visits required of research participants.

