Study participation for Study 1 and Study 2 will include a 24-week intervention evaluation period and a 12-week follow-up period for a total study duration of 36 weeks. Outcome assessments will be conducted at intake, every 4 weeks during the 24-week intervention period, and at a 12-week follow-up period.

Date: February 11, 2020

Principal Investigator: [name]

Application Number: IRB00186156

c. Blinding, including justification for blinding or not blinding the trial, if applicable.

Participants in Study 1 and Study 2 will not be blinded as to their study condition because participants in the incentive intervention cannot be blind to that intervention.

d. Justification of why participants will not receive routine care or will have current therapy stopped.

N/A

e. Justification for inclusion of a placebo or non-treatment group.

N/A

f. Definition of treatment failure or participant removal criteria.

Participants will be removed from either study if they threaten the safety of staff or other research participants, or of any other persons on the Johns Hopkins Bayview Campus.

g. Description of what happens to participants receiving therapy when study ends or if a participant's participation in the study ends prematurely.

Throughout Study 1 and Study 2, participants will be given referrals to services they might need (e.g., drug counseling, housing, medical, or employment services). Participants will continue to receive buprenorphine treatment as long as that treatment is available in the program they attend.

5. Inclusion/Exclusion Criteria

Study 1

Applicants will be invited to participate in this study if they: a) are \geq 18 years old, b) meet DSM-5 criteria for current opioid use disorder, c) provide an opioid-positive urine sample, d) report not receiving any type of drug abuse treatment in the past 30 days, and e) are interested in receiving buprenorphine treatment. Applicants will be excluded if they: a) have current suicidal/homicidal ideation, b) are pregnant or nursing, or c) are unwilling or unable to use a smartphone.

Study 2

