- a. Primary outcome variable.

Study 1 and Study 2 have the same primary outcome:

Specific aim. *Assess efficacy of Video DOT+ in promoting buprenorphine treatment adherence as assessed by urine drug screens.* We will assess the percentage of participants with buprenorphine-positive urine samples at the 4-week assessments during the 24-week intervention evaluation period (Yes/No at each assessment). Hypothesis: We expect that Video DOT+ participants will have more buprenorphine-positive urine samples during the 24-week intervention relative to the Usual Care Control participants.

- b. Secondary outcome variables.

Study 1 and Study 2 have the same secondary outcomes:

Specific aim. *Assess efficacy of Video DOT+ in promoting self-reported buprenorphine treatment*

Date: February 11, 2020

Principal Investigator: [name]

Application Number: IRB00186156

adherence. We will assess the number of days participants report taking their daily buprenorphine dose during the 30 days prior to each of the 4-week assessments during the 24-week intervention evaluation period (based on TLFB). *Hypothesis:* We expect that Video DOT+ participants will have more days of taking their buprenorphine dose as prescribed during the 24-week intervention relative to the Usual Care Control participants.

Specific aim. Assess efficacy of Video DOT+ in promoting linkage to buprenorphine treatment. We will assess the percentage of participants who link to buprenorphine treatment during the 24-week intervention evaluation period (Yes/No, based on self-report and medical records). *Hypothesis:* We expect that more Video DOT+ participants will link to buprenorphine treatment during the 24-week intervention relative to the Usual Care Control participants.

Specific aim. Assess efficacy of Video DOT+ in promoting retention in buprenorphine treatment. We will assess the total number of days participants are in buprenorphine treatment from the time of randomization until the last day of medication during the 24-week intervention evaluation period (based on self-report and medical records). *Hypothesis:* We expect that Video DOT+ participants will be retained in buprenorphine treatment for more days during the 24-week intervention relative to the Usual Care Control participants.

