Specific aim. Assess efficacy of Video DOT+ in reducing opioid use. We will assess the percentage of participants with opioid-positive urine samples (excluding buprenorphine and methadone if self-report and medical records confirm that the participant is enrolled in buprenorphine or methadone treatment) at the 4-week assessments during the 24-week intervention evaluation period (Yes/No at each assessment).

Hypothesis: We expect that Video DOT+ participants will have fewer opioid-positive urine samples during the 24-week intervention relative to the Usual Care Control participants.

Specific aim. Assess efficacy of Video DOT+ in reducing risk of opioid overdose. We will assess the rates at which participants report engaging in overdose risk behaviors at the 4-week assessments during the 24-week intervention evaluation period (based on total scores from the opioid overdose risk assessment).

Hypothesis: We expect that Video DOT+ participants will engage in lower rates of opioid overdose risk behaviors during the 24-week intervention relative to Usual Care Control.

Specific aim. Assess efficacy of Video DOT+ in promoting buprenorphine treatment engagement and adherence, and reducing opioid use and risk of opioid overdose after the intervention ends. We will assess these outcomes at the 12-week follow-up after the intervention ends. *Hypothesis:* We expect that Video DOT+ participants will have better buprenorphine treatment outcomes relative to the Usual Care Control participants after the intervention ends.

c. Statistical plan including sample size justification and interim data analysis.

Statistical Analyses

Separate statistical analyses will be conducted for Study 1 and Study 2, using the procedures described below.

We will analyze measures assessed repeatedly over time with a longitudinal logistic regression model. Within-person correlated outcomes will be handled using generalized estimating equations (GEE; Zeger, Liang, & Albert, 1988). Measures assessed once will be analyzed using logistic regression. The magnitude of effects will be expressed using odds ratios with 95% confidence intervals. Retention in buprenorphine treatment during the 24 weeks of the intervention period will be analyzed with a Cox proportional hazards model. We will adjust the intent-to-treat analyses for covariates used for stratification (Pocock, Assmann, Enos, & Kasten, 2002). Tests will be two-sided and, because we have one primary outcome, alpha will be set at 0.05.

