Primary outcome analyses. The primary outcome measure will be the percentage of participants with buprenorphine-positive urine samples at the 4-week assessments during the 24-week intervention

Date: February 11, 2020

Principal Investigator: [name]

Application Number: IRB00186156

[figure not shown]
evaluation period (Y/N at each assessment). We will fit a longitudinal logistic regression model $\text{logit}(Y_{ij}) = \beta_0 + \beta_1 tx + \beta_2 \cdot 3x_{2-3} + \varepsilon_{ij}$, where Y_{ij} is evidence of buprenorphine adherence for the i th person at the j th timepoint (6 visits over 24 weeks), β_1 is the covariate of interest representing the expected increase in log odds of evidence of buprenorphine adherence as a function of assignment to the treatment group, and β_2 are the coefficients for the 2 randomization covariates. We will fit models with time and time by treatment interactions secondarily. These models will allow us to look at change over time in buprenorphine adherence in each study arm.

Secondary outcome analyses. We will fit longitudinal logistic regression models, similar to those described for the primary outcome measure, for self-reported buprenorphine treatment adherence, opioid use, and opioid overdose risk behaviors. Linkage to buprenorphine treatment and post-intervention effects will be assessed by logistic regression. Retention in buprenorphine treatment during the 24 weeks of the intervention period will be analyzed with a Cox proportional hazards model.

Missing data. We expect to collect $\geq 85\%$ of the study assessments. Our primary approach to handle missing data will be to impute missing values as the adverse outcome (e.g., buprenorphine-negative urine sample). Model parameter estimates from this approach will be compared to a method without imputation. If these methods yield differing results, conclusions will need to be tentative, but results from both approaches will be reported in publications. To investigate sensitivity to missing values, participants with and without missing values will be compared by covariates and group assignment. If rates are higher than expected, we may use mixed effects models rather than GEE estimation, as the former has less strict assumptions regarding missing data (missing at random, rather than missing completely at random). If the data are missing not at random, then we will fit pattern mixture models as described by Hedeker and Gibbons (1997).

Power Analyses

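### The primary model omits intake buprenorphine urine status, the baseline value of the primary outcome; this may cost some power and leaves chance imbalance in it unadjusted

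*Combined protocol and SAP*

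**What the plan says.** Section 7a defines the primary outcome as the "percentage of participants with buprenorphine-positive urine samples at the 4-week assessments during the 24-week intervention evaluation period". Section 7c fits a longitudinal logistic model by GEE to the "6 visits over 24 weeks", with a treatment term and the "coefficients for the 2 randomization covariates". The general rule in the same section is: "We will adjust the intent-to-treat analyses for covariates used for stratification". In both studies (section 4a, Experimental Design) the urn randomization balances on sex and on whether the intake urine is positive for cocaine. Intake buprenorphine status appears in neither place.

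Section 4a lists urine toxicology among the instruments used both at intake and at the major assessments: "Urine samples will be collected under observation and tested for opioids and other drugs". The panel is not itemized. Section 5 requires applicants to "provide an opioid-positive urine sample" and to report no drug abuse treatment in the past 30 days. It does not require a buprenorphine-negative sample. The Background section on diversion cites a national survey in which "misuse of buprenorphine has increased substantially".

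**The concern.** When a binary outcome is measured repeatedly after randomization and the same measurement exists at baseline, the baseline value is a natural adjustment covariate. Here it should already be in hand: the intake urine supplies the cocaine result that feeds the urn, so it precedes assignment.

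Being out of treatment does not make every intake sample negative. Eligibility rests on self-report, and non-prescribed buprenorphine is in circulation. The opioid-use outcome in section 7b sets buprenorphine positives aside only where enrollment in treatment is confirmed, so the plan itself allows for positive samples from people not enrolled.

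At stake are some power in a study planned around 64 participants, and a treatment estimate that would carry any between-arm difference in intake status without correction. A covariate added after an imbalance has been seen would be post hoc, so the decision has to be made now.

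**Working it through.** **Inputs from the plan (section 7c).** Six post-randomization visits, two-sided alpha 0.05, 80% power, a 25-point difference, 64 randomized.

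**Inputs assumed, because the documents do not give them.** 1:1 allocation; control rate; within-person correlation rho; q, the share buprenorphine-positive at intake; dp, the difference in later positivity between intake-positive and intake-negative participants (or the corresponding odds ratio).

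**1. The plan's own figure.** With repeated binary outcomes and exchangeable correlation, n per arm = (1.960 + 0.842)² × [p1(1−p1) + p2(1−p2)] × (1 + 5·rho) / (6 × 0.25²). For 30% vs 55% the bracket is 0.21 + 0.2475 = 0.4575, so n = 57.45 × (1 + 5·rho)/6. Setting n = 32 gives rho = 0.47. Other control rates need rho = 0.55 (20%), 0.50 (25%) or 0.45 (40%). So 64 is attainable, but it can be neither confirmed nor refuted, because the control rate and correlation are not in the text.

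**2. Approximate gain from adjustment.** The variance of a person's six-visit mean is V = (0.4575/2) × (1 + 5 × 0.468)/6 = 0.127. The share explained by intake status is R² = dp² × q(1−q)/V. Adjusted power = Φ(0.25/√(2V(1−R²)/32) − 1.96). For q = 20% and dp = 0.3, R² = 0.09 × 0.16/0.127 = 0.113 and power is 84.5%, against 80% unadjusted.

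| q | dp 0.2 | dp 0.3 | dp 0.4 |
|---|---|---|---|
| 5% | 80.6% | 81.3% | 82.4% |
| 10% | 81.1% | 82.5% | 84.5% |
| 20% | 82.0% | 84.5% | 88.0% |
| 30% | 82.6% | 85.9% | 90.4% |

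If everyone is negative at intake, the gain is zero and the term cannot be estimated.

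**3. Simulations of the GEE, N=64, power without → with the intake term.**

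- A: 25% vs 50%, correlation 0.45, Kauermann-Carroll variance, t reference, 6,000 trials per setting. q/OR 10%/3: 77.6 → 79.1%. 20%/6: 74.9 → 82.6%. 30%/6: 74.3 → 84.1%.
- B: same rates, conditional correlation 0.40, independence GEE, leverage-corrected variance, t reference, 4,000 trials. 10%/3: 79.0 → 79.7%. 10%/6: 76.6 → 82.2%. 20%/3: 79.1 → 81.3%. 20%/6: 76.7 → 84.3%. 30%/6: 76.3 → 86.4%.
- C: 30% vs 55%, correlation 0.5, independence GEE, cluster-robust variance, stratification covariates left out, 1,500 trials. q/dp 5%/0.2: 76.7 → 77.2%. 10%/0.2: 77.0 → 76.8%. 20%/0.2: 74.2 → 76.9%. 20%/0.3: 72.2 → 76.5%. 30%/0.3: 74.7 → 79.3%.

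For q of 10-30% the changes run from −0.2 (essentially none) to +10.1 points. At the rates in A and B, an odds ratio of 3 corresponds to dp of about 0.22-0.27 and 6 to about 0.36-0.41, so the three sets broadly agree.

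**4. Type I error, without and with the term.** A (20%/6): 5.1% and 5.0%. B: 5.1% and 4.2%. C: 4.6-6.1% and 4.9-6.3%. Omission does not inflate it.

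**5. Chance imbalance, 32 per arm.** A gap of at least 10 points means at least 4 participants (4/32 = 12.5%). From two binomials, its probability is 4.5% at q = 5%, 14% at 10%, 27% at 20% and 34% at 30%. The SD of the gap is √(2q(1−q)/32): 5.4, 7.5, 10.0 and 11.5 points. With dp = 0.3, a 1-SD gap moves the 25-point contrast by 0.3 × SD, or 1.6, 2.3, 3.0 and 3.4 points.

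**6. Sparse positives.** At q = 10%, 1-3% of fits in A were unstable. In a further run of B at q = 5%, forcing the term in lowered power from 81.0% to 76.1%, with 12% of fits unstable. For 64 participants, the binomial probability of fewer than 5 positives is 78% at q = 5%, 22% at 10% and 0.2% at 20%.

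**The case against.** Adjusting for the stratification factors is a legitimate, prespecified choice with a methodological citation, and nothing in the plan is contradictory. Random imbalance is already reflected in the confidence interval. All of that stands.

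A reader might infer that the plan loses power as a matter of fact. The documents do not support this: they state neither q nor dp, and people who report no recent treatment may be nearly all negative at intake. A reader might also take the Background to say that non-prescribed use is widespread. It reports an increase in a national sample, which gives no prevalence for this Baltimore cohort. Nor do the documents show that intake status is the strongest predictor: an intake positive in someone out of treatment probably reflects non-prescribed use, whereas the outcome is meant to reflect adherence to treatment. And since buprenorphine is not named on the intake panel, the claim that no new data are needed is a reasonable inference only.

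The authors say that adding balancing variables is impractical at this sample size. That remark concerns stratification; one model term is a lighter burden, provided enough participants are positive. The objections that a third covariate changes the odds ratio being estimated, and that a rule for dropping it depends on the data, are sound. They call for a narrow change with a rule that ignores arm and outcome; they do not defeat the change.

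**Conclusion.** The point holds as a low-cost improvement in efficiency and robustness, not as an error in the plan. That the covariate is absent from both the model and the randomization is certain. The size of the benefit is not. At N=64, with 10-30% positive at intake and a moderate to strong link, it is about 0 to 10 points of power. Under the approximation and in simulation C, gains of about 4 to 6 points need roughly 20-30% positive and a 30-point difference in later positivity. At about 5% or below the benefit is negligible, and forcing the term in can do harm. The omission neither biases the randomized comparison nor inflates type I error. The figures rest on assumed control rates, within-person correlation, intake prevalence, strength of link and equal allocation.

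**What to change.** - Confirm in section 4a that buprenorphine is on the intake panel.
- In section 7c, prespecify the intake buprenorphine urine result (positive/negative) as a third covariate in the primary GEE and in the secondary models for buprenorphine adherence. Leave the opioid-use and overdose-risk models alone: this is not their baseline value.
- Fix a fallback before any comparison by arm, based on the count pooled over arms: for example, omit the term in a study if fewer than 5 participants are positive at intake.
- Report intake positivity by arm in each study.

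The cost is a line or two of text and, if the panel already includes buprenorphine, no new data. The downsides should be stated: the odds ratio becomes conditional on one more covariate, so it differs somewhat from one adjusted for sex and cocaine alone, and fits may be unstable when few participants are positive.

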Retention of patients in buprenorphine treatment. Although buprenorphine can reduce opioid use and protect against opioid overdose, many patients enrolled in office-based buprenorphine treatment do not remain in treatment (for systematic reviews, see Mattick et al., 2014; Timko et al., 2016). In a recent multi-site, randomized controlled trial conducted by the Clinical Trials Network (Lee et al., 2017), only 43% of participants remained in buprenorphine treatment over the 24-week trial. Rates of retention were similar in an earlier multi-site study with opioid-dependent adults, in which 46% of participants remained in buprenorphine treatment over a 24-week trial (Hser et al., 2014).

Addressing the limitations of office-based buprenorphine treatment. Office-based buprenorphine could be an ideal pharmacotherapy in the movement to expand access to treatment for opioid use disorder and thereby combat the opioid overdose epidemic, but it has two limitations that we plan to address in this

Date: February 11, 2020

Principal Investigator: [name]

Application Number: IRB00186156

application: 1) Buprenorphine that is prescribed by office-based providers can be easily diverted for illicit use. 2) Many people in dire need of buprenorphine treatment do not initiate and remain in office-based buprenorphine treatment.

Reducing Diversion through Video-Based Directly Observed Therapy (Video DOT)

Methadone maintenance programs minimize the risk of diversion by directly observing dosing in the methadone clinics. While effective in minimizing diversion, directly observed dosing is costly to both the providers and patients, and may be limited in scalability and long-term effectiveness. Office-based prescription of buprenorphine reduces the cost of administering opioid treatment medications for both the providers and patients and offers a means of dramatically increasing our capacity to treat people with opioid use disorder. Fortunately, mobile technology can facilitate directly observed dosing for buprenorphine treatment at a relatively low cost and thereby reduce the risk of diversion.

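### The repeated-measures model has no visit term, and neither the non-imputed comparison nor the mixed-model fallback is given one, so both can mix arm with time if positive rates change over the visits and the arms miss different visits

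*Combined protocol and SAP*

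**What the plan says.** Section 7c, Statistical Analyses, sets the method for repeated outcomes: "Within-person correlated outcomes will be handled using generalized estimating equations". Under Primary outcome analyses, the linear predictor holds an intercept, treatment and the two randomization covariates, for "6 visits over 24 weeks". It has no visit or time term. The next step is: "We will fit models with time and time by treatment interactions secondarily". Its stated purpose is to describe change over time within each arm. The repeated secondary outcomes get models of a similar form.

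The Missing data paragraph then makes three moves:

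- The primary rule: "Our primary approach to handle missing data will be to impute missing values as the adverse outcome (e.g., buprenorphine-negative urine sample").
- The robustness check: "Model parameter estimates from this approach will be compared to a method without imputation". If the two disagree, conclusions are to be tentative and both results are to be reported.
- The fallback, should missingness exceed what was planned for: "we may use mixed effects models rather than GEE estimation, as the former has less strict assumptions regarding missing data", namely missing at random rather than missing completely at random.

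At least 85% of assessments are expected to be collected. Neither the comparison nor the fallback restates the mean model.

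**The concern.** Once every missed visit is scored negative, both arms contribute all six visits and leaving out visit does not bias the treatment comparison. Without imputation that balance can go. An arm that loses more late visits has an observed average weighted towards early visits. If the positive rate changes over time, a model without visit attributes the difference in visit mix to treatment.

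The mixed model is offered because it needs only missing at random. That property belongs to a likelihood whose model for the data is right, including the mean at each visit. Where there is a time trend, a mean without visit is wrong and the protection is lost.

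What is at stake is the credibility check. The non-imputed result helps decide whether the conclusions become tentative, and an avoidable artefact should neither create nor hide a disagreement. The fallback would be used when missingness is high, which is when the artefact is larger.

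**Working it through.** **Inputs from the plan.** Six visits; mean model without visit; at least 85% of assessments collected; 64 randomized; 25-point design difference (Section 7c). The 64 cannot be reproduced from the text, because the control rate is varied in a figure and no within-person correlation is given. It is attainable: with a 20% control rate, correlation 0.5 and a pooled-variance form of the repeated-binary formula, it is 32 per arm. The figure is used below only to set a standard error.

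**Assumptions (not in the documents).** Visit-specific rates, missingness by arm and visit, 1:1 allocation, and a random-intercept SD of 2 on the logit scale. Stratification covariates are left out.

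**Step 1: closed form, no treatment effect at any visit.** With an independence working correlation and no visit term, an arm's fitted rate is Σ oⱼpⱼ / Σ oⱼ, where pⱼ is the positive rate and oⱼ the fraction observed at visit j.

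Example: p falls 0.60, 0.54, 0.48, 0.42, 0.36, 0.30. Control missingness rises from 5% to 45% and Video DOT+ stays at 5%, so 15% is missing overall.

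- Control: (0.95×0.60 + 0.87×0.54 + 0.79×0.48 + 0.71×0.42 + 0.63×0.36 + 0.55×0.30) / 4.50 = 2.109 / 4.50 = 0.4687.
- Video DOT+: 0.4500.
- Difference −1.87 points; OR = (0.4500/0.5500) / (0.4687/0.5313) = 0.928, where the truth is 1.

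The same formula for other patterns:

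| Positive rate | Missing: control; Video DOT+ | Overall | Difference (points) | OR |
|---|---|---|---|---|
| Flat 0.45 | 5→45%; 5% | 15% | 0.00 | 1.000 |
| 0.60→0.30 | 20% flat; 10% flat | 15% | 0.00 | 1.000 |
| 0.55→0.35 | 5→35%; 5→15% | 15% | −0.62 | 0.975 |
| 0.60→0.30 | 5→45%; 5% | 15% | −1.87 | 0.928 |
| 0.20→0.50 | 5→45%; 5% | 15% | +1.87 | 1.087 |
| 0.60→0.30 | 10→80%; 5→25% | 30% | −3.63 | 0.864 |
| 0.20→0.50 | 10→80%; 5→25% | 30% | +3.63 | 1.181 |

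Bias needs both a trend and a different visit profile by arm. A different overall rate of missingness is not enough (second row).

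**Step 2: simulation of the two 30% rows, 6,000 per arm, no effect.** Falling: exchangeable GEE OR 0.870 without visit and 1.017 with (complete data 1.008); mixed model 0.805 and 1.034. Rising: GEE 1.217 and 1.016 (complete data 1.016); mixed model 1.341 and 1.022.

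**Step 3: drop-out depending only on arm and last observed result.** Positives fall from 65% to 29%; 85% of visits are collected (74% control, 96% Video DOT+).

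- No effect: GEE 0.86 and mixed 0.80 without visit; both 1.00 with visit. Repeated runs gave GEE 0.83 to 0.86 without and 0.96 to 1.00 with.
- True effect of about 28 points, complete data against observed data within the same model: without visit, GEE 3.31 falls to 2.85 and mixed 6.00 to 4.66; with visit, GEE is 3.53 and 3.55, mixed 7.92 and 7.91.

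**Step 4: size at N=64 (500 replicates, falling 0.60→0.30, GEE).** Mean bias in log OR is −0.08 at 15% missing (SE about 0.35) and −0.14 at 30% (SE about 0.36). Type I error is 7.2% without visit against 6.0% with, and 6.4% against 5.0%. The Monte Carlo error is about 1 point, so these differences are not clear.

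**Step 5: how much of a disagreement visit explains.** In one run of the no-effect case of Step 3, the imputed OR was 1.26 and the non-imputed OR 0.83 without visit, 0.96 with. The log gap is ln(1.26/0.83) = 0.42, and ln(1.26/0.96) = 0.27 remains after adding visit. About two-thirds comes from scoring missing as negative.

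**The case against.** The strongest reply is that neither condition for bias is documented. Section 3 says of one outside trial that "only 43% of participants remained in buprenorphine treatment over the 24-week trial", and gives 46% for another. Those are 24-week retention figures for people in buprenorphine treatment, not urine results by visit. Participants here enter reporting no drug treatment in the past 30 days (Section 5), are referred, and may link at any time in the 24 weeks, so positives could rise, stay flat or fall. Both arms are paid $50 per assessment, and leaving buprenorphine treatment is not the same as missing a visit. This stands: a reader might infer that the omission understates the Video DOT+ effect, but the documents do not fix the direction.

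Second, models with time are already planned, the mean model of the comparison is not stated, and the mixed model is optional. This stands in part. Reuse of the model without time is the natural reading, since parameter estimates are to be compared and the fallback is described only as a change from GEE; it is not an explicit statement. Pre-specification would settle it.

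Third, the effect is small at the planned completeness. That also stands: at 15% missing, the bias at N=64 is about a quarter of a standard error (0.08/0.35).

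**Conclusion.** The point holds in a limited form. As naturally read, the non-imputed comparison and the mixed-model fallback omit visit. Both are then biased when positive rates change over the visits and the arms' missed visits are distributed differently, even if data are missing at random. In the closed-form scenarios the distortion is at most about 2 points at 15% missing and about 3.6 points at 30%, against a design difference of 25; steeper trends or more divergent drop-out would give more. The mechanism is certain; the size rests on the assumed rates, missingness patterns and random-intercept SD.

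Three stronger readings are not supported. The imputed primary result is not biased by this omission. Different missed visits alone do not cause bias; a time trend is also needed. And a disagreement between imputed and non-imputed results cannot be put down to visit alone, because part of it, the larger part in the no-effect case above, comes from scoring missing as negative.

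**What to change.** State in Section 7c that categorical visit (five indicators for six assessments) is included in the non-imputed comparison, in any mixed model used instead, and in the non-imputed or mixed-model versions of the repeated secondary outcomes. Fit the imputed model with the same visit terms, so that the estimates being compared have the same meaning; the imputed test does not otherwise need them. Keep the treatment coefficient as the single primary test and the time-by-treatment model as secondary.

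The cost is a line of text, five coefficients and a slightly different odds ratio, now conditional on visit (in the complete-data simulation, GEE 3.53 instead of 3.31; the mixed-model OR moves more, 7.92 instead of 6.00). In 250 simulated trials of N=64 with complete data, power was 87.2% without visit and 87.6% with. Visit terms do not remove GEE's stricter missing-data assumption, which the plan itself acknowledges, nor the effect of scoring missing as negative.
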